## **5. Research Design and Methods:**

**I): Materials:** All materials that will be used as well as their description, composition, and manufacturers are listed in (Table1).

**Table 1:** The materials brand names, description, compositions and manufacturers:

Material brand name	Description	Compositions	Manufacturers
STELA Primer	primer	10-MDP, dimethacrylates, methyl ethyl ketone (MEK), water, initiators, stabilizers.	
STELA	Self cured bioactive bulk fill resin based composite	Catalyst: barium- glass, glass, ytterbium trifluoride (YbF 3 ), silica, urethane dimethacrylate, initiators, stabilizers  Base: strontium fluoroaluminosilicate glass, ytterbium trifluoride agglomerates (YbF 3 ), silica, calcium aluminate (Al 2 CaO), urethane dimethacrylate, initiators, stabilizers	SDI Limited, Australia
Meta Etchant	Acid Etching gel	37% phosphoric acid, distilled water, and a colloidal Silica sol	Meta Biomed, Korea

All-bond uni-versal dental adhesive	One step self-etch adhesive	10-methacryloyloxydecyl dihydrogenphosphate , Bisphenol A glycidyl dimethacrylate, 2-hydroxyethyl methacrylate, Ethanol, Water, Initiators	Bisco, INC Schaumburg, IL, USA
Filtek™ Z250 XT	Nano-hybrid resin composite	Matrix: Bis-GMA, UDMA, Bis- EMA. Filler: Inorganic fillers : zirconia, silica 78.5 wt % 63.3 vol%	3M ESPE St.Paul,M, USA

## II: Methods:

### II- 1 Study Setting:

A randomized controlled double-blinded clinical trial will be conducted where both patient and examiners will be blinded to the group assignment. Patients of age group 21–45 years (**Hirani et al, 2018**) will be selected where each patient should have two ocluso- mesial cavities. Patients will be recruited from the outpatient clinic of Conservative Dentistry department in the Faculty of Dentistry, Suez Canal University. During the initial examination, the purpose and the method of the research will be explained to the patients and a written informed consent will be assigned by each individual.

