### **II-3 Cavity preparation:**

The same treatment protocol will be followed for all patients where each patient will receive two compound class II cavities in posterior molar teeth distributed in both sides. Local anesthesia will be administered in the beginning of the session and quadrant isolation will be administrated by rubber dam. Access through enamel and outline form will be obtained with a sterile high speed #245 bur. Following the international guidelines, all soft infected dentine will be removed, and a hard sound dentin floor should be reached. For the peripheries of the cavity, carious tissue removal to hard dentine will be performed using a sharp sterile spoon double-ended excavator and a low-speed round bur. The dentinoenamel junction, cavosurface margins and gingival box will be inspected carefully and to be clean, with at least 1.5 to 2 mm rim of peripheral sound tooth structure to provide a firm marginal adhesion for the restoration.

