## II-5 Restorative procedures:

Each included patient with the already prepared cavities will receive two different types of restorations. where one of them will be restored with light cured nano hybrid RBC (Filtek™ Z250, 3M ESPE St.Paul,M,USA) (M1) meanwhile, the second cavity will be restored with self-cure bioactive RBC (Stela, SDI, Australia) (M2).

A sectional matrix system will be used to achieve proper proximal contour and anatomically correct contact with the adjacent tooth. Then, the restorative procedure of each cavity will be carried out according to the manufacturer's recommendations of each tested restoration. Before restoration each cavity will be carefully cleaned with copious air water spray before being dried. Restoration of (M1) group will be performed through selective etching of the prepared cavity enamel surface using 37% phosphoric acid gel (Meta Biomed, Korea) for 15 seconds. This will be followed by rinsing with water for 15 seconds and gentle air drying for 5 seconds, leaving the cavity slightly moist. After that, single layer of a universal adhesive bonding agent (Bisco, INC Schaumburg, IL, USA) will be applied to the prepared cavity walls and floor using disposable adhesive micro brush. The adhesive will be subsequently cured for 20 seconds using LED light curing unit (Elipar S10, 3M ESPE, St Paul, Minnesota, USA) with an intensity of 1200 mW/cm^2. The nano hybrid RBC (Filtek™ Z250) will be incrementally applied, and light cured according to manufacturer instructions. Finally, finishing and polishing of the restoration using one-step polishing system (Dimanto, Voco, Germany). Then, checking of occlusion and proximal contacts will be done.

Restoration of (M2) group will be performed through conditioning of cavities with a specialized primer (STELA primer, SDI, Australia) according to manufacturer instructions. Then, a self cured bioactive RBC (STELA, SDI, Australia) will be placed in a single increment and allowed to self-cure according to manufacturer instructions. Then, finishing and polishing of the restoration, checking the occlusion and proximal contacts will be done as mentioned before.

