#### **II-7- Assessment of the bioactivity:**

Bioactivity of each examined restoration will be determined by the evaluation of mineral density beneath the tested materials. Immediately after restoration (D0), an image plate digital sensor (Xios XG Supreme, Dentsply Sirona, UK) will be used for transmitting the radiographic

image of the selected tooth to the computer. A posterior parallel kit will be used for image standardization. Later, each restoration will be examined at standardized follow-up periods; one month (D1) and three months (D2) (Table 4 and 5). The image plate will be inserted at one end of the parallel kit, while the other end was connected to the x-ray cone. All the radiographs will be evaluated for the outcome by a software (ImageJ software, NIH, USA). The assessment of mineral density will be done by the software through performing the following measurements: in each image a line will be drawn along the CEJ to act as a reference, while another parallel line will be drawn at the bottom of the cavity. The distance between both lines will be standardized for each tooth by measuring the length of a vertical line connecting them. The length of the line centralized at the bottom of the cavity will be determined in pixels directly via the previously mentioned software. Such length will be fixed for each sample throughout assessment intervals. Three points on this line (at its start, middle and end) will be determined. The mineral density value at each of these points will be identified by taking the corresponding three readings from the software and recording them to calculate the average value. The mineral density mean value will be calculated from the software (Ibrahim et al, 2016).

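### The double-blind label is not supported: the patient blind is not credible given the two restorative procedures, and the protocol describes nothing that secures the examiner blind for the radiographs.

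*Protocol*

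**What the plan says.** Section II-1 (Study Setting) describes a randomised, double-blinded trial in which "both patient and examiners will be blinded to the group assignment". The same section says that at the first examination "the purpose and the method of the research will be explained to the patients". Section 7 adds that consent covers the examinations, procedures and follow-up.

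Section II-3 gives each patient two cavities, one on each side of the mouth, treated under rubber dam: "Local anesthesia will be administered in the beginning of the session". No sedation is mentioned.

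Section II-5 sets out two different procedures:

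- **M1 (nanohybrid):** "Restoration of (M1) group will be performed through selective etching of the prepared cavity enamel surface using 37% phosphoric acid gel". Then, after bonding, "The adhesive will be subsequently cured for 20 seconds using LED light curing unit". The composite follows in light-cured increments.
- **M2 (bioactive):** a primer, after which the composite "will be placed in a single increment and allowed to self-cure according to manufacturer instructions".

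For mineral density, section II-7 has the reader draw a reference line at the cemento-enamel junction (CEJ), and "another parallel line will be drawn at the bottom of the cavity". The distance between the two lines is standardised for each tooth, the line length is fixed across visits, and three points on it are averaged. Table 1 lists M2 fillers that include barium glass and "strontium fluoroaluminosilicate glass, ytterbium trifluoride agglomerates"; for M1 it lists zirconia and silica.

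**The concern.** A double-blind claim tells readers that neither the patient's behaviour nor the reading of outcomes could be influenced by knowing the material. Here the two treatments are delivered side by side in the same conscious person by visibly different steps, so the patient part of the claim conflicts with the procedures.

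The examiner part matters more for the results. Mineral density is a grey-value reading at points that a person positions beneath a restoration visible on the same image. Section 4.d records the expectation that the bioactive material will do markedly well on bioactivity, so any expectation effect has a known direction. If the reader's masking is not secured, the trial report would claim a protection against bias that the plan does not provide.

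**Working it through.** No sample size, power or event count enters this point, so there is no planned figure to reproduce. The check sets the sections side by side.

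**1. Patient blind**

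| Feature | M1 tooth | M2 tooth | Source |
|---|---|---|---|
| Anaesthesia | local | local | II-3 |
| Side of mouth | one side | the other side | II-3 |
| Air-water cleaning | yes | yes | II-5 |
| Acid etch of enamel | 15 s, then 15 s rinse | none written | II-5 |
| LED cure of adhesive | 20 s | none written | II-5 |
| Composite placement | light-cured increments | one self-cured increment | II-5 |
| Sham light step | not applicable | none written | II-5 |

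The rinse is a weak clue, because both cavities are sprayed with air and water. The curing light is a strong one: it is used repeatedly on one side and never on the other. Section 3 frames the research question as self-cured against light-cured composite, and II-1 says the purpose and method are explained beforehand. A patient so informed needs only to notice which side received the light.

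**2. Examiner blind, radiographs**

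- Number of images: 12 patients x 2 teeth x 3 times (D0, D1, D2) = 72. With the 10 per group that remain after the allowed dropout, 10 x 2 x 3 = 60.
- Controlled by II-7: the parallel kit, the CEJ-to-floor distance for each tooth, the line length, and the three averaged points.
- Left to the hand: drawing the CEJ line on each image, the horizontal position of the measuring line, and the first placement of the floor line against the restoration.
- Possible clue to the material: the fillers differ, but Table 1 gives no radiopacity for either product and no filler percentage for M2. M1 also contains a radiopaque filler, zirconia. A visible difference may exist; its presence and size cannot be derived from the document.
- Safeguards described in II-4 to II-7: no assessor separate from the operator, no coding, no cropping or masking, no random reading order.

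**3. Examiner blind, scans**

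Section II-6 obtains volume loss by software superimposition. Nothing there reveals the material to the reader, and nothing there describes coding either.

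**The case against.** The best defence has four parts.

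First, II-1 blinds examiners, not the operator, and an independent reader given coded images could be kept unaware of the material. This stands. The examiner blind is unsupported, not contradicted.

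Second, II-7 already constrains the reading well. This stands in part: the standardised CEJ-to-floor distance limits vertical drift between visits. A reader might infer that the line is redrawn freely at every visit with only its length held; the text does not support that. What remains is the hand-drawn CEJ line, the horizontal position and the first placement.

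Third, the exact information given to patients is not visible, because the consent pages are not part of the text at hand. This is fair, and the conclusion therefore rests on II-1, section 7 and the research question. A patient told nothing about curing would find it harder to name the material, but would still notice that the two sides were treated differently.

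Fourth, both outcomes are instrument-based and no patient-reported outcome is planned, so a patient's knowledge has limited reach. This also stands. Favouring one side when chewing is a conceivable route to a difference in wear, but the document offers no evidence for it.

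Two stronger readings are tempting. One is that the radiograph reader will recognise the material; without radiopacity values, that is only possible. The other is to express the bias as a share of the planned effect size of 1.22. The document gives no placement error from which to start, and the sample-size section does not tie that effect size to mineral density.

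**Conclusion.** The point holds in two grades. For patients, the blind claimed in II-1 is not credible as written, because II-3 and II-5 describe a conscious patient who receives two distinguishable procedures with no sham step. This assumes that explaining the method includes how each material is cured. For examiners, the blind is asserted without any procedure to secure it, and the exposure is greatest for the hand-placed part of up to 72 density readings. Nothing in the document unmasks the scan reader.

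A reader might conclude that no blinding at all is achievable in this trial. That goes too far: assessor blinding is feasible with ordinary file handling. The size of any bias cannot be stated from the document. The correction should be made before reading begins, since it concerns both a claim that will appear in the report and a measurement that can still be protected.

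**What to change.** 1. In II-1, replace the double-blinded label with: outcome-assessor-blinded; patients and operator not blinded. Name by role who reads the radiographs and scans, and state that this person did not place the restorations.
2. Give every radiograph and scan file a code, remove dates and visit labels, and read them in random order. The code list is held by someone who does no readings.
3. Set the measuring line once on each tooth's D0 image and transfer it to D1 and D2 by registration on unrestored tooth structure, instead of placing it again by hand.
4. Where feasible, mask the restoration pixels above the line before grey values are read.

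The treatment procedures stay as they are. The changes need protocol wording, file coding and a registration and masking step, using the software already planned (ImageJ and Geomagic) and existing staff. The price is a weaker blinding label and some image-preparation time.

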### II-2 Sample Selection:

Patients participating in this study will be selected according to the following eligibility criteria:

**II-2-a Inclusion Criteria: (Hirani et al, 2018).**

1. Patients with vital two molar teeth with compound class II deep carious lesions.
2. Both males and females will be included.
3. Patients with good general health.
4. Patients with good oral hygiene.
5. Co-operative patients.
6. Absence of spontaneous pain, mobility or tenderness on percussion.
7. Radiographically: no internal or external resorption, no periapical or furcation radiolucency and no widening of the periodontal ligament space.

**II-2-b Exclusion Criteria: (Hirani et al, 2018).**

1. Patients with systemic decease.
2. Patients with severe or chronic periodontitis.
3. Patients have allergy to the materials used in this trial.
4. Nonfunctioning teeth.
5. Teeth with any pathologic pulpal changes .
6. Teeth with previous restorations.
7. Teeth with surface loss due to non carious lesions .

All patients who will attend the clinic will receive the proposed treatment protocols. However, only those who will meet the inclusion criteria will be enrolled in the study and included in the trial. Patients who

will not fulfill the inclusion criteria will also be treated but will be excluded from the study analysis.

### **II-3 Cavity preparation:**

The same treatment protocol will be followed for all patients where each patient will receive two compound class II cavities in posterior molar teeth distributed in both sides. Local anesthesia will be administered in the beginning of the session and quadrant isolation will be administrated by rubber dam. Access through enamel and outline form will be obtained with a sterile high speed #245 bur. Following the international guidelines, all soft infected dentine will be removed, and a hard sound dentin floor should be reached. For the peripheries of the cavity, carious tissue removal to hard dentine will be performed using a sharp sterile spoon double-ended excavator and a low-speed round bur. The dentinoenamel junction, cavosurface margins and gingival box will be inspected carefully and to be clean, with at least 1.5 to 2 mm rim of peripheral sound tooth structure to provide a firm marginal adhesion for the restoration.

### **II-4 Randomization:**

To minimize selection bias and ensure equal distribution of treatment protocol across both treated molars, simple randomization will be used to randomly determine which molar receives which material. Therefore, randomization will be performed using an online randomization tool (<https://www.randomizer.org/>) prior to treatment allocation where, each patient will be given a unique study number, ensuring that each patient receives both treatments in a randomly assigned manner.

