#### Methodology:

Twelve healthy patients with 24 carious molar teeth will be selected where each patient should have two ocluso- mesial cavities. Standardized

occluso- mesial cavities will be prepared for all the selected teeth, for each patient the first tooth will be restored with conventional nanohybrid RBC (M1). Meanwhile, the second tooth will be restored by self-cure bioactive RBC (M2). Then, wear resistance will be evaluated by intraoral scanner immediately after restoration (T0), six months later (T1), after 12 months (T2), 18 months (T3) and 24 months (T4). Software analysis will be done by superimposing the 3D digital impression and evaluate the restoration wear by calculating the 3D volume loss.

Also, bioactivity of the restoration will be measured by measuring the mineral density beneath the restoration. Digital radiographic images will be taken for the restoration by parallel technique and grey scale of the pixels under restoration will be measured by software immediately after restoration (D0), one month later (D1) and after 3 months (D2).

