## 6- Sample size calculation:

Sample size calculation was performed using G\*Power version 3.1.9.2, (Faul *et al*, 2007) University Kiel, Germany. Copyright (c) 1992-2014.

$$f = \frac{\sigma_\mu}{\sigma}$$

[figure not shown]
$$\sigma_\mu^2 = \frac{\sum_{i=1}^k n_j (\mu_i - \mu)^2}{N}$$

Where:

$f$ : is the effect size;  $\alpha = 0.05$ ;  $\beta = 0.05$ ; Power =  $1 - \beta = 0.80$

The effect size  $d$  was **1.22 (large)** according to the previous studies (**Elderiny et al., 2024**) with alpha ( $\alpha$ ) level of 0.05 and Beta ( $\beta$ ) level of 0.05, i.e., power = 80%; the estimated sample size ( $n$ ) should be **20** samples and will be divided into **two groups**.

To account for dropouts, the sample size will be expanded by 20%, which produced 12 restorations for each group instead of 10.

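### Simple randomisation cannot deliver the equal distribution of materials over the two molars that the protocol claims; with 12 patients an unequal split by position is the usual result

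*Protocol*

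**What the plan says.** The Abstract (Methodology) sets the size and the pairing: "Twelve healthy patients with 24 carious molar teeth will be selected where each patient should have two ocluso- mesial cavities". Section II-4 makes the claim at issue: to "ensure equal distribution of treatment protocol across both treated molars, simple randomization will be used to randomly determine which molar receives which material". It then says that each patient gets a study number, "ensuring that each patient receives both treatments in a randomly assigned manner". No blocking, stratification or other balancing constraint is stated anywhere.

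On where the teeth lie, section II-3 says that "each patient will receive two compound class II cavities in posterior molar teeth distributed in both sides". The inclusion criteria (II-2-a) ask only for "Patients with vital two molar teeth with compound class II deep carious lesions", so arch and first or second molar are neither restricted nor matched within a patient.

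The Abstract describes assignment differently. It says that "for each patient the first tooth will be restored with conventional nanohybrid RBC (M1") and that the second tooth receives the bioactive material (M2), without mentioning a random order.

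The Statistical analysis section plans independent t-tests or Mann-Whitney tests between the groups at each time, with no term for tooth position.

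**The concern.** The protocol claims a property that its method does not have. Every patient does receive both materials, but how often M1 lands on the right or the left molar is left to chance, and with 12 patients that chance variation is large.

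Pairing removes differences between patients. What differs within a patient, besides the material, is the tooth: its side, and possibly its arch and type. If one position wears faster than the other in a consistent direction, an unequal split moves part of that difference into the material comparison. Balanced allocation removes this component, and the planned analysis does not adjust for it.

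**Working it through.** **Inputs.** There are 12 patients with two molars each (Abstract, Methodology). This agrees with the sample size section, where 10 per group expanded by 20% is 10 × 1.2 = 12. Assignment is by independent 50:50 draws (II-4). The planned effect size is d = 1.22 (sample size section: "1.22 (large) according to the previous studies"), used here only as a yardstick. The protocol gives no figure for balance by position, so there is none to reproduce.

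**Distribution of splits.** Let k be the number of patients whose molar in a given position receives M1. Then k is Binomial(12, 0.5), and there are 2^12 = 4096 equally likely lists.

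**Effect on the estimate.** Suppose the given position differs from the other by δ in the same direction in every patient. The within-patient difference M1 − M2 then contains +δ in k patients and −δ in 12 − k. Its mean is shifted by δ × [k − (12 − k)]/12 = δ × (2k − 12)/12.

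| Split (either direction) | Lists of 4096 | Probability | Share of δ carried |
|---|---|---|---|
| 6:6 | 924 | 22.6% | 0 |
| 7:5 | 1584 | 38.7% | 17% |
| 8:4 | 990 | 24.2% | 33% |
| 9:3 | 440 | 10.7% | 50% |
| 10:2 | 132 | 3.2% | 67% |
| 11:1 | 24 | 0.6% | 83% |
| 12:0 | 2 | 0.05% | 100% |

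- Not equal: 1 − 924/4096 = 77.4%.
- 8:4 or worse: (990 + 440 + 132 + 24 + 2)/4096 = 1588/4096 = 38.8%.
- 9:3 or worse: 598/4096 = 14.6%.
- Mean signed shift: zero, by symmetry.
- Mean absolute shift: (1584 × 1/6 + 990 × 1/3 + 440 × 1/2 + 132 × 2/3 + 24 × 5/6 + 2 × 1)/4096 = 924/4096 = 0.226 δ.

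**Size for a range of δ.** The documents give no δ. The values below are assumptions, in the same SD units as d.

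| Assumed δ | Mean absolute shift | Shift at 8:4 | Shift at 9:3 |
|---|---|---|---|
| 0 | 0 | 0 | 0 |
| 0.25 SD | 0.06 SD (5% of 1.22) | 0.08 SD (7%) | 0.13 SD (10%) |
| 0.5 SD | 0.11 SD (9% of 1.22) | 0.17 SD (14%) | 0.25 SD (20%) |

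**With dropout to 10 patients.** Under simple randomisation, 5:5 has probability 24.6%, and 7:3 or worse 34.4%. A list that began at 6:6 and lost two patients is at worst 6:4, which carries (6 − 4)/10 = 20% of δ.

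**The case against.** The wording of II-4 can be read benignly: equal distribution may mean only that each patient has one molar per material, 12 and 12 overall. That equality is real, but it comes from the split-mouth pairing, and II-4 states it separately at its end. The sentence at issue is about which molar receives which material, and there simple randomisation guarantees nothing. If the benign meaning was intended, the error is one of wording and deleting the claim cures it.

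A reader might infer that the design confounds material with tooth position, or that the allocation is biased. The documents do not support this. A fair toss within each pair is a valid randomisation, the expected shift is zero, and complete confounding (12:0) has probability 0.05%. In a paired analysis a position effect also widens the spread of the within-patient differences, so it is reflected in the standard error.

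A reader might also take 20% of the planned effect as the likely damage. That figure combines a split of 9:3, reached or exceeded in 14.6% of lists, with one assumed δ of 0.5 SD. At the same δ the mean absolute shift is about 9%. Nothing in the documents shows a consistent right-left difference in wear or mineral density.

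Nor would a right-left list balance everything that may differ between the two teeth. Chewing preference varies between patients and stays a matter of chance. Arch and molar type also stay unbalanced unless the list provides for them.

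Finally, the Abstract's first and second tooth might be read as a fixed assignment. It could equally be loose labelling, since the document does not say what first refers to.

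**Conclusion.** The claim of equal distribution in II-4 is wrong as written. With 12 patients and independent tosses the split by position is unequal in 77.4% of lists and 8:4 or worse in 38.8%. These figures need only the patient number and the stated method.

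The consequence is chance imbalance, not bias in expectation. Its mean absolute size is 0.226 δ, where δ is a position effect in a common direction across patients; it is unknown and may be near zero for right versus left. The right-left reading also assumes one molar on each side in every patient, as II-3 suggests. The point is minor to moderate in weight, but it should be corrected because the text promises a property that a different list would supply at almost no cost.

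**What to change.** 1. In II-4, define the position to be balanced: right or left, and also arch or molar type if the two teeth may differ in these.
2. Replace simple randomisation with a list generated in advance: six patients with M1 on the right and six with M1 on the left, in random order, or permuted blocks with the same result. Conceal it from the person placing the restorations until assignment. Alternatively, keep simple randomisation and delete the claim of equal distribution.
3. Reconcile the Abstract's first-tooth and second-tooth wording with the random assignment in II-4, so that one rule stands.
4. If position is to be adjusted for, first replace the independent tests in the Statistical analysis section with a within-patient (paired) analysis, and include position in it.

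**Cost.** A different list and a few changed sentences, with no added patients, visits or measurements. The last allocations of a balanced list are slightly more predictable, which matters little when every patient receives both materials. Dropout can still disturb the 6:6 split, and chewing preference remains unbalanced.
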